Appendix 2 List of Permitted and Prohibited Prior/Concomitant Medications

Prohibited medications are shown in [Listing 1](#), [Listing 2](#), [Listing 3](#), [Listing 4](#), [Listing 5](#), and [Listing 6](#). Medications permitted with restrictions are listed in [Listing 7](#), [Listing 8](#), and [Listing 9](#). **These may not be all-inclusive listings.** Please contact the medical monitor(s) if the investigators have any questions or concerns regarding any medication not listed that your subjects may be taking before enrollment or start during the course of the E2609-G000-202 study.

Antibiotics, analgesics, and anti-inflammatory drugs intended for short courses of treatment are permitted and do not need to follow the restrictions of [Listing 9](#) for a stable dose of 4 weeks before Baseline. If these medications may affect cognitive function but the medications are clinically indicated, then cognitive testing should not take place until at least 72 hours after the last dose of the course of treatment.

Prohibited Prior/Concomitant Medications

Listing 1 Drugs with High Risk of Torsades de Pointes or QTc Prolongation

| Generic name | Brand name (Names shown are not exhaustive and are examples only; names may be the ® or ™) | Comments |
|---|--|---|
| Prohibited from 14 days (or 5 half-lives, whichever is longer) before Randomization until after the last treatment visit | | |
| Anti-arrhythmic/ abnormal heart rhythm | | |
| Amiodarone | Cordarone; Pacerone | Incidence in females greater than males, Torsades de Pointes risk regarded as low |
| Disopyramide | Norpace | Incidence in females greater than males |
| Dofetilide | Tikosyn | |
| Ibutilide | Corvert | Incidence in females greater than males |
| Procainamide | Pronestyl; Procan | |
| Quinidine | Cardioquin; Quinaglute | Incidence in females greater than males |
| Sotalol | Betapace | Incidence in females greater than males |
| Antihistamine/ allergic rhinitis | | |
| Astemizole | Hismanal | No longer available in United States |
| Terfenadine | Seldane | No longer available in United States |
| Anti-anginal/ heart pain | | |
| Bepridil | Vascor | Incidence in females greater than males |
| Antibiotic/ bacterial infection | | |
| Clarithromycin | Blaxin | |
| Moxifloxacin | Avelox | |
| Sparfloxacin | Zagam | |
| Listing 1 continued | | |
| Antimalarial/ malaria infection | | |
| Chloroquine | Aralen | |
| Halofantrine | Halfan | Incidence in females greater than males |
| Antipsychotic/ anti-emetic/ schizophrenia/ nausea | | |
| Chlorpromazine | Thorazine | |
| Gastrointestinal stimulant/ heartburn | | |
| Cisapride | Propulsid | |
| Antinausea/ nausea | | |

Listing 1 Drugs with High Risk of Torsades de Pointes or QTc Prolongation

| Generic name | Brand name (Names shown are not exhaustive and are examples only; names may be the ® or ™) | Comments |
|--|--|---|
| Domperidone | Motillum | Not available in the United States |
| Sedative; antinausea/ anesthesia adjunct, nausea | | |
| Droperidol | Inapsine | |
| Antibiotic; gastrointestinal stimulant/ bacterial infection; increase gastrointestinal motility | | |
| Erythromycin | Erythrocin; E.E.S. | Incidence in females greater than males |
| Antipsychotic/ schizophrenia | | |
| Haloperidol | Haldol | When given intravenously or at higher than recommended doses, risk of sudden death, QT prolongation, and torsades increases |
| Mesoridazine | Serentil | |
| Thioridazine | Mellaril | |
| Opiate agonist/ pain control, narcotic dependence | | |
| Levomethadyl | Orlaam | |
| Methadone | Methadose; Dolophine | Incidence in females greater than males |
| Anti-infective/ pneumocystis pneumonia | | |
| Pentamidine | Pentam; NebuPent | Incidence in females greater than males |
| Antipsychotic/ Tourette's tics | | |
| Pimozide | Orap | Incidence in females greater than males |
| Antilipemic/ hypercholesterolemia | | |
| Probucol | Lorelco | No longer available in United States |
| Anticancer | | |
| Arsenic trioxide | Trisenox | Used for leukemia |
| Vandetanib | Zactima | Used for thyroid cancer |

Note: This list is not exhaustive.

QTc = Corrected QT interval.

Listing 2 Prohibited Medications Within 7 Days (or 5 Half-lives, Whichever is Longer) Before Randomization and Until after the Last Treatment Visit)

| Generic Name | Brand name (Names shown are not exhaustive and are examples only; names may be the ® or ™) |
|---|---|
| Anticoagulants | |
| Adeporin | Normiflo |
| Alteplase, tPA | Activase, Cathflo Activase |
| Anisindione | Miradon |
| Antithrombin III | ATryn, Thrombate III |
| Argatroban | Argatroban |
| Bivalirudin | Angiomax |
| Dabigatran | Pradaxa |
| Dalteparin | Fragmin |
| Danaparoid | Orgaran |
| Dicumarol | Dicumarol |
| Enoxaparin | Lovenox |
| Fondaparinux | Arixtra |
| Heparin Sodium | Monoject |
| Lanoteplase | Lanoplase |
| Lepirudin | Refludan |
| Pentosan polysulfate sodium | Elmiron |
| Reteplase | Retavase, Retevase |
| Staphylokinase | Eskinase, Heberkinasa Kabikinase, Streptase, Thrombosolv, Zykinase |
| Streptokinase | Streptase |
| Tenecteplase | TNKase |
| Tinzaparin | Innohep |
| Urokinase | Abbokinase, Kinlytic |
| Warfarin | Coumadin, Jantoven |
| Antiplatelet drugs | |
| Aspirin and Plavix (revised per Amendment 01) | 
For subjects who consent to CSF sample collection: Aspirin or clopidogrel is permitted in all subjects. Aspirin and clopidogrel in combination is not permitted. (revised per Amendments 01 and 02)
 
For subjects who do not consent to CSF sample collection: Aspirin and clopidogrel, individually or in combination, is permitted. (revised per Amendment 02)
 |

Note: This list is not exhaustive.

Listing 3 Prohibited Medications Within 5 Half Lives or 60 Days, Whichever is Longer, Before Randomization and Until after the Last Treatment Visit

| Generic name | Brand name (Names shown are not exhaustive and are examples only; names may be the ® or ™) |
|---|--|
| Systemic Immunosuppressants^a and Immunomodulatory therapy | |
| Azathioprine | Azasan, Imur |
| Ciclosporine | Gengraf, Neoral |
| Dexamethasone | Decadron, Dexasone, Diodex, Hexadrol, Maxidex |
| Fingolimod | Gilenya |
| Methotrexate | Trexall |
| Methylprednisolone | Medrol, Meprolone |
| Mycophenolate | CellCept, Myfortic |
| Prednisolone | Deltasone, Prednicot, Prednisone Intensol, Rayos, Sterapred, Sterapred DS |

Note: This list is not exhaustive.

a: Topical and inhaled formulations with minimal systemic exposure need not be prohibited.

Listing 4 Prohibited Medications Within 6 Months Before Randomization

| Generic name | Brand name (Names shown are not exhaustive and are examples only; names may be the ® or ™) |
|---|---|
| Immunoglobulin therapy | |
| Adalimumab | Humira |
| Bevacizumab | Avastin |
| Efalizumab | Raptiva |
| Etanercept | Enbrel |
| Immune globulin IV, IVIG, IGIV | Carimune, Flebogamma, Gamimune N, Gammagard, Gamunex, Gammar-P IV, Iveegam, Octagam, Panglobulin, Vigam, Polygam S/D, Privigen, Sandoglobulin, Venoglobulin-S |
| Infliximab | Remicade |
| Omalizumab | Xolair |
| Ranibizumab | Lucentis |
| Other monoclonal antibodies not listed here | |

Note: This list is not exhaustive.

Listing 5 Prohibited Live Vaccines Within 3 Months Before Randomization Until after the Last Treatment Visit (this does not apply to non-live/inactivated vaccines)

| Bacterial vaccines | Viral vaccines |
|---|---|
| Bacillus Calmette-Guérin vaccine against tuberculosis | Measles vaccination |
| Cholera vaccination (oral) | Rubella vaccination |
| | Oral polio vaccination (Sabin) |
| | Yellow fever vaccination |
| | Varicella (chickenpox) vaccination |
| | Rotavirus vaccination |
| | Japanese encephalitis vaccination |
| | Live attenuated influenza vaccine (FluMist, Fluenz) |
| Typhoid vaccination (oral) | Mumps vaccination |

Note: This list is not exhaustive

**Listing 6 Strong CYP3A4 Inhibitors Prohibited Within 5 Half-Lives or 14 Days
(Whichever Is Longer) Before Randomization Until After the Last Treatment Visit**

| Generic name | Brand name(s) |
|---------------------|--|
| boceprevir | Victrelis |
| clarithromycin | Clarithromycin, clarithromycin extended release, Prevpac |
| cobicistat | Tybost, Stribild, |
| conivaptan | Vaprisol |
| danoprevir | |
| elvitegravir | Vitekta, Stribild |
| indinavir | Crixivan |
| itraconazole | Sporanox, Onmel |
| ketoconazole | Xolegel, Nizoral, Ketodan |
| lopinavir | Kaletra |
| nefazodone | Serzone |
| nelfinavir | Viracept |
| posaconazole | Noxafil |
| ritonavir | Norvir, Kaletra |
| saquinavir | Invirase, Fortovase |
| telaprevir | Incivek |
| telithromycin | Ketek |
| tipranavir | Aptivus |
| troleandomycin | Triocetin |
| voriconazole | Vfend, Voriconazole |

Note: This list is not exhaustive

Permitted Prior/Concomitant Medications

Listing 7 Medications Which Need To Be on a Stable Dose for 12 Weeks Before the Baseline Cognitive Assessments at Visit 2 and Remain on the Same Stable Dose from Baseline to Follow-Up Visit 2

| Generic name | Brand name (Names shown are not exhaustive and are examples only; names may be the ® or ™) |
|----------------------------|--|
| Cognitive Enhancers | |
| Donepezil | Aricept |
| Galantamine | Reminyl |
| Memantine | Namenda |
| Rivastigmine | Exelon |

Note: This list is not exhaustive.

Listing 8 Permitted Medications Used on PRN Basis Which are Not to be Used Within 72 Hours before Cognitive Testing

| Generic name | Brand name (Names shown are not exhaustive and are examples only; names may be the ® or ™) |
|---|---|
| Opiates | |
| Morphine | Astramorph PF, Avinza, Depo Dur, Duramorph, Infumorph, Kadian, MS Contin, MSIR, Oramorph SR, RMS, Roxanol |
| Opiate Agonists | |
| Codeine | Codeine |
| Fentanyl | Actiq, Duragesic, Fentora, Onsolis, Sublimaze |
| Meperidine | Demerol, Meperitab |
| Oxycodone | Dazidox, Endocodone, Eth-OxyDose, OxyContin, OxyFast, OxyIR, Percolone, Roxicodone, Roxicodone Intensol |
| Other opioids or opioid agonists which are used on PRN basis | |
| Benzodiazepines and sedatives | |
| Alprazolam | Alprazolam Intensol, Niravam, Xanax |
| Amitriptyline | (various) |
| Chlordiazepoxide | H-Tran, Librium |
| Clonazepam | Ceberclon, Klonopin |
| Diazepam | Diastat, Dizac, Valium |
| Dothiepin | (various) |
| Estazolam | ProSom |
| Flunitrazepam | Rohypnol |
| Flurazepam | Dalmane |
| Lorazepam | Ativan |
| Midazolam | Versed |
| Olanzapine | Zyprexa |
| Promethazine | Phenergan; others |
| Ramelteon | Rozerem |
| Risperidone | Risperdal |
| Temazepam | Restoril |
| Triazolam | Halcion |
| Zolpidem | Ambien; others |
| Zopiclone | (various) |
| Other benzodiazepines, tricyclic antidepressants, antipsychotics and other drugs which are used on PRN basis as sedatives | |

Note: This list is not exhaustive

PRN = Pro re nata

Listing 9 Permitted Centrally Active or Psychiatric Medications

| Generic Name | Brand name (Names shown are not exhaustive and are examples only; names may be the ® or ™) |
|--|--|
| If to be used on a PRN basis see Listing 8 . If to be used chronically, subjects must be on a stable dose for ≥4 weeks before Baseline. Changes in dose or initiation of new concomitant medications for chronic use (not PRN use) is permitted but if the medication affects cognitive function, do not conduct cognitive testing until the dose is stable for 4 weeks. | |
| Antidepressants | |
| Amitriptyline hydrochloride | Elavil |
| Amoxapine | Amoxapine |
| Bupropion | Aplenzin, Budeprion, Buproban, Zyban, Wellbutrin |
| Citalopram | Celexa |
| Clomipramine hydrochloride | Anafranil |
| Desipramine hydrochloride | Norpramin |
| Desvenlafaxine | Pristiq |
| Doxepin hydrochloride | Prudoxin, Silenor, Sinequan, Zonalon |
| Duloxetine | Cymbalta |
| Escitalopram | Lexapro |
| Fluoxetine | Prozac, Sarafem, Selfemra |
| Fluvoxamine | Luvox |
| Imipramine hydrochloride | Tofranil |
| Isocarboxazid | Marplan |
| Maprotiline hydrochloride | Ludiomil |
| Mirtazapine | Remeron Soltab |
| Nortriptyline hydrochloride | Aventyl, Pamelor |
| Paroxetine | Paxil, Pexeva |
| Phenelzine | Nardil |
| Protriptyline hydrochloride | Vivactil |
| Rasagiline | Azilect |
| Selegiline | EMSAM |
| Sertraline | Sertaraline, Zoloft |
| Tranlycypromine | Parnate |
| Trazodone hydrochloride | Desyrel, Oleptro |
| Trimipramine maleate | Surmontil |
| Venlafaxine hydrochloride | Effexor |

Listing 9 Permitted Centrally Active or Psychiatric Medications

| Generic Name | Brand name (Names shown are not exhaustive and are examples only; names may be the ® or ™) |
|---|--|
| Mood Stabilizers (Listing 8 continued) | |
| Carbamazepine | Carbatrol, Epitol, Equetro, Tegretol, Tegretol XR |
| Lamotrigine | Lamictal, Lamictal CD, Lamictal ODT, Lamictal XR |
| Valproic acid | Depacon, Depakene, Depakote, Depakote ER, Divalproex Sodium, Stavzor, Valproate |
| Antipsychotics | |
| Acetophenazine | Tindal |
| Aripiprazole | Abilify |
| Asenapine | Saphris |
| Olanzapine | Zyprexa |
| Chlorpromazine | Thorazine |
| Haloperidol | Haloperidol, Haldol |
| Clozapine | Clozaril, Fazaclo |
| Fluphenazine | Prolixin |
| L-Methylfolate | Deplin, L-Methylfolate Calcium |
| Loxapine | Loxitane |
| Mesoridazine | Serentil |
| Perphenazine | Trilafon |
| Quetiapine | Seroquel |
| Risperidone | Risperdal |
| Thioridazine | Mellaril |
| Thiothixene | Navane |
| Trifluoperazine | Stelazine |
| Benzodiazepines | |
| Alprazolam | Alprazolam Intensol, Niravam, Xanax |
| Chlordiazepoxide | H-Tran, Librium |
| Clonazepam | Ceberclon, Klonopin |
| Diazepam | Diastat, Dizac, Valium |
| Estazolam | ProSom |
| Flunitrazepam | Rohypnol |

Listing 9 Permitted Centrally Active or Psychiatric Medications

| Generic Name | Brand name (Names shown are not exhaustive and are examples only; names may be the ® or ™) |
|--------------|--|
| Flurazepam | Dalmane |
| Lorazepam | Ativan |
| Midazolam | Versed |
| Temazepam | Restoril |
| Triazolam | Halcion |
| Zopiclone | Imovane, Zimovane |
| Zopidem | Ambien, Ambien CR, Intermezzo, Stilnox, Stilnoct, Sublinox, Hypnogen, Zolsana |

Note: This list is not exhaustive.

PRN = Pro re nata

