9.4.7 Prior and Concomitant Therapy

Medication (including over-the-counter medications) or therapy administered to the subject before the study (within 6 months of randomization) and during the study (starting at the date of informed consent) will be recorded on the Prior & Concomitant Medication eCRF or Non-Pharmacological Procedures eCRF. The investigator will record on the Adverse Event eCRF any AE for which the concomitant medication/therapy was administered. If the concomitant medication/therapy is being administered for a medical condition present at the time of entry into the study, the investigator will record the medical condition on the Medical History and Current Medical Condition eCRF.

Listings of prohibited and permitted drugs are provided in [Appendix 2](#). Prohibited medications are presented in [Listing 1](#), [Listing 2](#), [Listing 3](#), [Listing 4](#), [Listing 5](#), and [Listing 6](#). Medications that are permitted with restrictions are listed in [Listing 7](#), [Listing 8](#), and [Listing 9](#).

The following agents are not permitted before randomization (specific timeframes are shown below) and throughout the study until after the last treatment visit:

- Anticoagulants (eg, warfarin, digabatin) are not permitted for a period of 5 half-lives or 7 days (whichever is longer) before randomization
- Drugs which may cause QTc prolongation are not permitted for a period of 5 half-lives or 14 days (whichever is longer) before randomization
- Strong CYP3A4 inhibitors are not permitted for a period of 5 half-lives or 14 days (whichever is longer) before randomization
- Live vaccines are not permitted within 3 months before randomization. This does not apply to non-live/inactivated vaccines
- Ig therapy and biologic drugs are not permitted within 6 months before randomization

- Systemic or ocular immunosuppressive or immunomodulatory drugs are not permitted for a period of 5 half-lives or 60 days (whichever is longer) before randomization

Subjects taking AChEIs or memantine must meet the following criteria in order to be included in the primary analyses:

- On a stable dose for 12 weeks before the Baseline cognitive assessments at Visit 2
- Remain on a stable dose while on study

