Subjects who initiate treatment with an AChEI or memantine during the study, or who change their dose of AChEI or memantine while on study, will be allowed to continue in the study, but their clinical efficacy data will be censored from the time of drug initiation for the primary analyses.

Subjects taking all other non-prohibited concomitant medications must meet the following requirements:

- Must be on stable dose for at least 4 weeks before randomization, except for medications that are administered as short courses of treatment or which are to be used intermittently as needed
- Medications that are used as needed, rather than on a stable daily basis, and which are central nervous system (CNS) active and may affect cognitive function, are not permitted during a period of 72 hours before cognitive testing

Subjects who initiate treatment with or have dose adjustment of drugs not intended for treatment of cognitive impairment during the study may continue in the study if in the opinion of the investigator this will not interfere with study procedures or subject safety, and are not prohibited above. If the subject initiates treatment for co-morbidities with a (non-prohibited) drug that may affect cognitive function, the subject should not have cognitive assessments performed until the dose has been stable for at least 4 weeks.

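### Appendix 2 permits by name in Listing 9 four antipsychotics that Listing 1 prohibits for torsades or QTc risk; Listing 9 is the list to correct

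*Protocol*

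**What the plan says.** **Listing 1** (Appendix 2) covers drugs with a high risk of torsades de pointes or QTc prolongation. Its rule is "Prohibited from 14 days (or 5 half-lives, whichever is longer) before Randomization until after the last treatment visit". Chlorpromazine, haloperidol, mesoridazine and thioridazine are among its entries. The haloperidol row reads "Haloperidol | Haldol | When given intravenously or at higher than recommended doses, risk of sudden death, QT prolongation, and torsades increases"; the comment cells for the other three are blank.

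**Listing 9** (Appendix 2) covers permitted centrally active or psychiatric drugs. Its antipsychotic section names the same four, including the row "Haloperidol | Haloperidol, Haldol". Its header asks for at least 4 weeks on a stable dose before Baseline for chronic use, and adds: "Changes in dose or initiation of new concomitant medications for chronic use (not PRN use) is permitted".

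**Listing 8** (Appendix 2), for drugs used as needed, ends with a catch-all row: "Other benzodiazepines, tricyclic antidepressants, antipsychotics and other drugs which are used on PRN basis as sedatives". It does not except Listing 1 drugs.

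**Section 9.4.7** states that "Drugs which may cause QTc prolongation are not permitted" for 14 days or 5 half-lives before randomization, under a lead-in that carries the ban through treatment. It lets other drugs be started if, in the investigator's opinion, "this will not interfere with study procedures or subject safety, and are not prohibited above". The same section also points sites to Listings 7 to 9: "Medications that are permitted with restrictions are listed in" those listings.

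**Section 9.3.2**: criterion 25 excludes subjects who use QT-prolonging medication, and criterion 37 excludes violations of the concomitant-medication restrictions.

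**The concern.** A drug cannot be both prohibited until after the last treatment visit and permitted for chronic use or new initiation. Site staff use the listings as look-up tables, and one that names a drug as permitted gives an explicit yes. Staff who check one of these four against Listing 9 alone could accept a subject who is taking it, or let it be started during treatment, and so breach a safety rule written in the same appendix.

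The appendix's own safety net does not catch this. Its opening paragraph sends investigators to the medical monitor about drugs that are not listed, and these four are listed.

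What is at stake is torsades exposure in an elderly population for which the protocol already excludes QTc above 450 msec, together with avoidable eligibility and concomitant-medication deviations across about 125 sites. The efficacy analysis is not at stake, and there is no claim that the randomized ECG comparison is confounded.

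**Working it through.** No power, alpha or sample-size figure is involved. The check is a match of generic names, followed by a search for any text that would reconcile the two tables.

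**1. Match Listing 1 against Listing 9.** Listing 1 has 30 generic names. Exactly four are also in Listing 9:

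| Drug | Listing 1 | Listing 9 |
|---|---|---|
| Chlorpromazine | prohibited, no comment | permitted |
| Haloperidol | prohibited, comment on intravenous or high-dose use | permitted |
| Mesoridazine | prohibited, no comment | permitted |
| Thioridazine | prohibited, no comment | permitted |

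**2. Size of the overlap.**
- Listing 1 places five agents under a heading that includes antipsychotic use: chlorpromazine, haloperidol, mesoridazine, thioridazine and pimozide. All but pimozide are in Listing 9: 4/5.
- The antipsychotic section of Listing 9 has 17 rows: 4/17.

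**3. Is it an artefact of comparing versions?** No. The overlap lies within the Version 3.0 appendix, and again within the appendix that carries Amendment 02 text. The rows are intact in both.

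**4. Does any text reconcile the tables?** The haloperidol comment says when the risk rises; it exempts no dose or route. The other three drugs have no comment. Neither listing has a footnote on the point, and Appendix 2 has no rule on which listing prevails.

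**5. Which listing is wrong?** Section 9.4.7 bars QTc-prolonging drugs before randomization and throughout treatment, and makes new starts conditional on the drug not being prohibited. Criterion 25 excludes users of such drugs at entry. Both agree with Listing 1, and nothing in the body supports an exception for these four. Listing 9 is therefore the error.

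**6. How far do the ECGs mitigate?** Table 7 schedules treatment-period ECGs at Visits 5, 7, 9, 11, 14, 16 and 18, which are weeks 2, 4, 8, 12, 26, 52 and 78. The longest gaps are 52 − 26 = 26 weeks and 78 − 52 = 26 weeks. A drug started just after the week 26 or week 52 ECG could go about 26 weeks without a scheduled ECG. The QTcF stopping rules in Section 9.3.3 act only when an ECG is taken.

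**7. QTc signal of the study drug.** Section 7.1 reports a QTcF increase of 14.9 msec at 4 hours after a single 800 mg dose. The top dose here is 50 mg, so the nominal-dose ratio is 800/50 = 16. This is not an exposure margin: Section 9.4.4 says that the tablet given with food has a higher AUC and a lower peak than the fasted capsule. It shows only that the reported signal was small and came at a much larger nominal dose.

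**The case against.** The strongest reply is that the governing text is clear and the appendix row is a slip. To enrol such a subject, a site would have to overlook criterion 25, criterion 37, Section 9.4.7 and Listing 1. Criterion 6, which excludes confounding psychiatric symptoms such as hallucinations or delusions, probably makes chronic antipsychotic use at entry less common. New starts are allowed only for drugs that are not prohibited, and triplicate ECGs with QTcF stopping rules add detection.

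Much of this stands. It settles the intent and makes the enrolment route less likely than a start during treatment. It does not remove the contradiction: Section 9.4.7 itself sends sites to Listing 9 as a list of permitted drugs, and Listing 9 does not repeat the condition that the drug must not be prohibited.

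Three narrower points also have weight:
- The revision history shows nefazodone moved from Listing 9 to Listing 6 because it is a strong CYP3A4 inhibitor. The same revision introduced that prohibition, and nothing shows that nefazodone stood in two conflicting listings. It is an analogy, not an identical case.
- The catch-all row in Listing 8 names none of the four and is limited to as-needed sedative use. It is a gap worth closing, not a second contradiction.
- The body text that accompanies the Amendment 02 appendix is not available here, so for that version the statement of intent is carried over from Version 3.0.

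**Conclusion.** The contradiction is real, and Listing 9 is wrong as written. Four drugs are both prohibited and permitted by name: 4 of the 5 antipsychotic-headed agents in Listing 1, and 4 of the 17 antipsychotic rows in Listing 9, in both appendix versions shown.

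The consequence is a modest, unquantified risk to patient safety and protocol adherence, partly mitigated by the entry criteria, Section 9.4.7, the ECGs and the stopping rules. The document does not allow an estimate of how many subjects would be affected. No endpoint, error rate or sample size depends on it.

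The conclusion that Listing 9, not Listing 1, is the mistake rests on criteria 25 and 37 and Section 9.4.7 of Version 3.0, and on the assumption that these did not change in the later body text. The point should be fixed because it touches a stated safety rule and the correction is nearly free.

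**What to change.** 1. Delete chlorpromazine, haloperidol, mesoridazine and thioridazine from Listing 9.
2. Add one sentence to Appendix 2: where a drug appears in Listing 1, or belongs to a class permitted in Listing 8 or 9, the Listing 1 prohibition prevails, including for as-needed antipsychotics under the Listing 8 catch-all row.
3. Send sites a clarification letter.

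The cost is four table rows removed, one sentence added and one letter. Design and analysis stay as they are.
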